2.2 Hypotheses and/or Estimations

The primary hypothesis is that SC evolocumab will be well tolerated when added to standard of care in pediatric subjects 10 to 17 years of age with HeFH or HoFH.

3. Study Overview

3.1 Study Design

This is an open-label, single-arm, multicenter study. Subjects are eligible for screening if they have completed Study 20120123 (and did not experience a treatment-related serious adverse event) or if they are 10 to 17 years of age at time of enrollment and have HoFH. The minimum expected enrollment of HeFH (rollover) subjects is approximately 70% of subjects enrolled in Study 20120123 or approximately **111** subjects. In addition, approximately 10 subjects with HoFH (and without prior participation in an evolocumab study) will be enrolled for an expected total enrollment of approximately **124** subjects. Depending on willingness of 20120123 subjects to continue evolocumab administration, final enrollment may be smaller or greater.

Where permitted by local regulations, the study includes collection of biomarker development samples and subjects will be invited to consent/assent to pharmacogenetic analyses.

3.2 Sample Size

Approximately **124** subjects are anticipated to enroll in this trial. This corresponds to an estimated 70% rollover for subjects with HeFH from the parent study 20120123 and approximately 10 subjects with HoFH enrolling in this study. Depending on rollover rate from study 20120123, final enrollment may be smaller or greater.

3.3 Adaptive Design

Not applicable.

4. Covariates and Subgroups

4.1 Planned Covariates

No planned covariates will be included in the analysis.

4.2 Subgroups

No subgroup analysis will be included in the analysis.

5. Definitions

5.1 Study Timepoints

Enrollment Date

The enrollment date is defined as the date collected on the Subject Enrollment eCRF.

Study Day 1

For each subject, Study Day 1 is defined as the first day of investigational product administration. If a subject never received IP, then Study Day 1 is defined as the date of enrollment.

Study Day

For each subject, and for a given date of interest, study day is defined as the number of days since Study Day 1:

Study day = (date of interest – Study Day 1 date) + 1.

If the date of interest is prior to the Study Day 1:

Study day = (date of interest – Study Day 1 date), so that the day prior to Study Day 1 is study day -1.

First Dose Date of Investigational Product

For each subject, the First Dose Date of Investigational Product is defined as the first administration date of the IP as recorded on the IP administration eCRF.

Last Dose Date of Investigational Product

For each subject, the Last Dose Date of Investigational Product is defined as the date of the last administration of the IP:

If the last dose was administered in-clinic, then the Last IP Dose Date is the last start date captured on the IP Administration (In-Clinic) eCRF page.

If the last dose was administered at a non-investigator site location, then the Last IP Dose Date is defined as the final dose date reported by the subject on the Non-Clinic Final Investigational Product Dose Date eCRF page.

End of Study (EOS) Date for Each Subject

End of study for each subject is defined as the last day on which the enrolled subject in this study completes the end-of-study visit (week 80) or terminates the study early. The date will be recorded on the End of Study eCRF page.

Study End Date for the Overall Study

The study end date is defined as the date when the last enrolled subject has completed the end-of-study visit (week 80) (ie, last subject last visit).

5.2 Demographics and Baseline Related Definitions

Age at Enrollment

Age will be collected as the subject's age in years at enrollment as recorded on the eCRF.

Baseline Lipid and Lipid-related Parameters

For subjects with HeFH rolling over from parent study 20120123, baseline lipid and lipid-related parameters are defined as parent study baseline lipid and lipid-related parameters. For lipids (total cholesterol, HDL-C, LDL-C, VLDL-C and triglycerides), ApoA1, ApoB, hsCRP, Lp(a) and their derived parameters (eg, ratio between them) of de novo subjects with HoFH, the baseline values are defined as the mean of the two most recent non-missing concentrations measured through central lab prior to or on Study Day 1. If for any reason only 1 value is available, then that value will be used as baseline for de novo subjects.

Other Baseline Values

For subjects with HeFH rolling over from parent study 20120123, other baseline values (ECG, PCSK9, and other variables) are defined as parent study baseline values.

For de novo subjects with HoFH, the baseline ECG value is defined as the mean over all non-missing triplicate averages of 3 (or all available) readings from each set of triplicate taken prior to or on Study Day 1. For PCSK9, the baseline value is defined as the average of the last two non-missing values collected prior to first IP administration. If for any reason only 1 value is available, then that value will be used as baseline. For all other variables, the baseline value is defined as the last non-missing value collected prior to first IP administration.

Change (absolute change) from Baseline

The arithmetic difference between a post-baseline value and baseline for a given time point:

Change (absolute change) from baseline = (post-baseline value – baseline value)

Percent Change from Baseline

The percent change from baseline for a given variable at a given time point is defined as:

$100 \times [(value\ at\ given\ time\ point - baseline\ value) / baseline\ value]$

Baseline Metabolic Syndrome

For each subject without type 2 diabetes mellitus, metabolic syndrome is identified by the presence of 3 or more of the components listed below (modified AHA/NHLBI criteria, [Fryar et al 2012](#), [Ji et al 2010](#)). Subjects with type 2 diabetes cannot be categorized as having metabolic syndrome.

Age 10 to <16 years

Risk Factor	Defining Level
Elevated waist circumference:	Obesity > 90 percentile or adult cut-off if lower (refer to the cut-offs below)
Non-Asian (Fryar et al., 2012):	
Male:	
Age 10	>85.6 cm
Age 11	>90.4 cm
Age 12	>93.7 cm
Age 13	>96.7 cm
Age 14	>101.3 cm
Age 15	>99.9 cm
Female:	
Age 10	> 84.1 cm
Age 11	> 88 cm
Age 12	> 88 cm
Age 13	> 88 cm
Age 14	> 88 cm
Age 15	> 88 cm
Asian (Ji et al, 2010):	
Male:	
Age 10	> 73.1 cm
Age 11	> 75.6 cm
Age 12	> 77.4 cm
Age 13	> 78.6 cm
Age 14	> 79.6 cm
Age 15	> 80.5 cm
Female:	
Age 10	> 67.8 cm
Age 11	> 70.4 cm
Age 12	> 72.6 cm
Age 13	> 74.0 cm
Age 14	> 74.9 cm
Age 15	> 75.5 cm
Triglycerides	> 1.7 mmol/L (150 mg/dL)
HDL cholesterol	<1.03 mmol/L (40 mg/dL)
Blood pressure	SBP > 130 mmHg or DBP > 85 mmHg OR Hypertension checked 'yes' on CV Medical History eCRF
Fasting glucose	> 5.6 mmol/L (100 mg/dL) or known type 2 diabetes mellitus

For Age \geq 16 years

Risk Factor	Defining Level
Elevated waist circumference:	
Non-Asian:	
Male	\geq 102 cm
Female	\geq 88 cm
Asian:	
Male	\geq 90 cm
Female	\geq 80 cm
Triglycerides	\geq 150 mg/dL
HDL cholesterol	
Male	$<$ 40 mg/dL
Female	$<$ 50 mg/dL
Blood pressure	SBP \geq 130 mmHg or DBP \geq 85 mmHg OR Hypertension checked 'yes' on CV Medical History eCRF
Fasting glucose	\geq 100 mg/dL

Baseline CHD Risk Factors

A subject will be categorized as having 2 or more CHD Risk Factors (Y/N) from the list of the modified NCEP ATP III risk factors:

- current cigarette smoking
- hypertension
- type II diabetes mellitus
- family history of premature CHD as recorded on the eCRF
- low HDL-C defined as baseline HDL-C $<$ 40 mg/dL for both males and females with age 10 to $<$ 16 years; $<$ 40 mg/dL in male and $<$ 50 mg/dL in female with age \geq 16 years.

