1.3 Secondary Safety

- To describe change from baseline in steroid hormones and the subject incidence of abnormal muscle and liver enzyme levels after 80 weeks of SC evolocumab, added to standard of care in pediatric subjects 10 to 17 years of age with HeFH or HoFH
- To describe changes from baseline in carotid intima-media thickness (cIMT) after 80 weeks of SC evolocumab, added to standard of care in pediatric subjects 10 to 17 years of age with HeFH or HoFH
- To describe change from baseline in growth and pubertal development parameters at measured timepoints with 80 weeks of SC evolocumab, added to standard of care in pediatric subjects 10 to 17 years of age with HeFH or HoFH

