2.4 Rationale

FH is a genetic disorder which typically requires lifelong treatment, sometimes beginning in childhood. Therefore, it is important to study the long-term safety and efficacy of potential treatments for FH in children and adolescents. Because developmental processes that are complete in adults are ongoing in children and adolescents, additional safety assessments (eg, biochemical and clinical assessments of puberty; carotid intimal medial thickness; cognition) are appropriate.

The safety and efficacy of evolocumab 420 mg SC QM in adults have been extensively studied in phase 2 and phase 3 clinical trials. Additionally, in the two studies that have included pediatric subjects (Studies 20110233 and 20110271), evolocumab lowered LDL-C and other lipid parameters in subjects aged 12-17 years. At the time of enrollment in Study 20120124, subjects with HeFH will have completed the double-blind, placebo-controlled study 20120123 in which they will have been randomized to evolocumab or placebo for 24 weeks. Study 20120124 is designed to provide longer-term clinical experience with evolocumab in subjects 10 to 17 years of age. The primary endpoint of Study 20120124 is the incidence of treatment emergent adverse events at week 80. Assessments of several lipid parameters, including LDL-C, Lp(a), non-HDL-C, ApoB, total cholesterol/HDL-C ratio, and ApoB/ApoA1 ratio were chosen as additional endpoints to evaluate stability of the treatment effect over the duration of the study.

Pharmacokinetic data from the 2 studies with evolocumab that included adults as well as pediatric subjects age 12 years and older (Studies 20110233 and 20110271) show that exposure among pediatric subjects is comparable to that seen in adults of similar weight. Further pharmacokinetic modeling to predict the optimal dosing regimen for pediatric subjects 10 to 17 years of age shows that the exposure with monthly administration of 420 mg evolocumab SC in these subjects is expected to fall within the range already observed in the evolocumab development program.

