7.2 General Study Procedures

It is the responsibility of the investigator to ensure that all procedures are performed according to the protocol. Written informed consent must be obtained before protocol specific procedures are carried out. The risks and benefits of participating in the study will be verbally explained to each potential subject prior to entering into the study. The procedures to be performed are described below and the timing of the procedures is provided in [Table 2](#).

Subjects must be fasting for ≥ 9 hours before each study visit where fasting samples are being taken. For procedures if the subject is not fasting when presenting at the study site for a visit, please see [Section 7.2.1.2](#) and [Section 7.2.2](#) below. If IP is administered during a study visit, administration must be after completion of all other visit procedures, including vital signs, ECG, Cogstate testing, cIMT imaging, blood draw procedures, and apheresis. Apheresis is permitted only for subjects with HoFH; blood draw procedures are to occur before apheresis.

All on-study visits and dosing should be scheduled from study day 1. Day 1 and week 80 visits must be scheduled at approximately the same time of day, and should be performed as close as possible to 8 am as the hormones measured have diurnal variation. Weeks are counted from day 1, the first day of IP administration, eg, the week 4 visit is 4 weeks after the study day 1 visit, corresponding to study day 29. When it is not possible to perform the study visit at the specified time point, the visit should be performed within the visit window as specified in the Schedule of Assessments ([Table 2](#)). If a study visit is missed or late, including visits outside the visit window, subsequent visits should resume on the original visit schedule. Missed assessments at prior visits should not be duplicated at subsequent visits. With the exception of screening and rescreen visits (HoFH subjects only), all study procedures for a visit must be completed on the same day.

Demographic data including sex, age, race, and ethnicity will be collected in order to study their possible association with treatment effectiveness, subject safety, or, for example, to further study biomarker variability.

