10.4 Planned Methods of Analysis

10.4.1 General Considerations

Statistical analyses in this open label study are descriptive in nature. No statistical inference or missing value imputation is planned.

Subject disposition, demographics and baseline characteristics will be summarized.

Summary statistics for continuous variables will include the number of subjects, mean, median, standard deviation or standard error, minimum, and maximum. For categorical variables, the frequency and percentage will be given.

For efficacy analyses, the baseline value is defined as:

- Subjects that participated in parent Study 20120123 and with baseline data from the parent study: the baseline is defined as the baseline of the qualifying parent study.
- Subjects not enrolling from a parent study or without baseline data from the parent study: the baseline is defined as the baseline in this study.

Subjects will be summarized according to whether subject rolled over from a parent study and their treatment allocation from a parent study when applicable.

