9.6.3 Analyses of Secondary Safety Endpoints

Descriptive statistics of change from baseline will be provided for the following safety parameters at week 80.

- Steroid hormone levels (FSH, LH, ACTH, DHEA-S, cortisol, estradiol in females, testosterone in males).
- Carotid intima-media thickness (cIMT)

Summary of subject incidence of abnormal muscle and liver enzymes at week 80 will also be provided.

Abnormalities of muscle and liver enzymes will be assessed by the following categories:

- CK > 5 x ULN
- CK > 10 x ULN
- ALT or AST > 3 x ULN
- ALT or AST > 5 x ULN
- Total bilirubin \geq 2 x ULN
- (ALT or AST > 3 x ULN) and (Total bilirubin > 2 x ULN) and Alkaline Phosphatase < 2 x ULN

Descriptive statistics of change from baseline in growth (height and weight) will be provided at week 24, 48 and 80 by study cohort, parent study treatment and gender.

Shift from baseline in Tanner staging at weeks 24, 48 and 80 will be summarized by study cohort, parent study treatment and gender.

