9.6.6 Physical Measurements

Physical measurements will be summarized using descriptive statistics at each scheduled visit.

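### For HeFH rollovers, growth, Tanner and hormone changes are measured only from the parent-study baseline, so visits labelled week 24/48/80 nominally cover 48/72/104 weeks, 24 of them on placebo in former-placebo subjects

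*SAP*

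**What the plan says.** The SAP sets different baselines for the two cohorts. For HeFH rollovers, "other baseline values (ECG, PCSK9, and other variables) are defined as parent study baseline values" (section 5.2). No exception is made for safety variables, so the rule reaches height, weight, Tanner stage and hormones. For de novo HoFH subjects and the same variables, "the baseline value is defined as the last non-missing value collected prior to first IP administration" (section 5.2).

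The visit clock is the same for everyone: "Weeks are counted from day 1, the first day of IP administration" (Protocol 7.2). SAP 5.1 and Appendix A follow it. On reaching that day, rollovers have already spent a parent-study period in which "they will have been randomized to evolocumab or placebo for 24 weeks" (Protocol 2.4).

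The growth objective is "To describe change from baseline in growth and pubertal development parameters at measured timepoints with 80 weeks of SC evolocumab" (Protocol 1.3). SAP 9.6.3 plans the height and weight changes so that they "will be provided at week 24, 48 and 80 by study cohort, parent study treatment and gender". It plans Tanner shifts at the same visits with the same split, and hormone changes at week 80.

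The protocol's own parent-baseline rule opens with "For efficacy analyses, the baseline value is defined as" (section 10.4.1). It gives no rollover baseline rule for safety variables.

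**The concern.** In 10 to 17 year olds, height, weight, pubertal stage and sex hormones change with the passage of time alone. A change in these variables can be read only if the interval behind it is known. Here the interval for a HeFH subject is longer than the visit name suggests, and no planned table says so. A HoFH column beside it under the same visit name runs on a different time scale.

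The former-placebo arm matters most. These are the rollovers for whom a drug-free starting value exists at the start of open-label dosing, so they can show change over the open-label evolocumab period from a pre-drug value. With the parent baseline as the only reference, each of their growth, Tanner and hormone changes includes the placebo period. What is at stake is the reading of named secondary safety endpoints in about 111 HeFH subjects, out of 121 (111 + 10) to 124 planned.

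**Working it through.** **Inputs**
- Parent treatment period: 24 weeks (Protocol 2.4).
- Rollover at the parent week 24 visit, so the nominal gap g is 0 (Protocol 3.5.1). Table 2 footnote b provides for gaps above 4 weeks and states no upper limit.
- Growth and Tanner visits: w = 24, 48, 80. Hormones: w = 80 only (SAP 9.6.3, Protocol Table 2).
- Assumption: these variables were measured at parent baseline. The parent protocol is not supplied.

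**Reproducing the plan's own figures.** Target day = 7w + 1 gives 169, 337 and 561 for weeks 24, 48 and 80. These match SAP Appendix A, which confirms that the labels count from open-label Day 1.

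**Interval behind each label**
- From parent baseline: 24 + g + w.
- Share off evolocumab in former-placebo subjects: (24 + g) / (24 + g + w).

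| Visit label | HeFH interval, g = 0 | Ratio to label | Off-drug share, former placebo | HoFH interval |
|---|---|---|---|---|
| Week 24 | 24 + 24 = 48 | 2.0 | 24/48 = 50% | 24 |
| Week 48 | 24 + 48 = 72 | 1.5 | 24/72 = 33% | 48 |
| Week 80 | 24 + 80 = 104 | 1.3 | 24/104 = 23% | 80 |

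Only the last row applies to hormones. In calendar terms, 104 weeks is 104 × 7 / 365.25 × 12 = 23.9 months, against 18.4 months for 80 weeks. In former-evolocumab subjects with no gap, the 104 weeks are nominally all on evolocumab.

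**Sensitivity**
- With an assumed 4-week gap the intervals are 52, 76 and 108 weeks. The off-drug shares are 28/52 = 54%, 28/76 = 37% and 28/108 = 26%.
- In the other direction, the Appendix A hormone window runs from after Day 1 to end of study. An early-termination value can therefore be assigned to week 80, which shortens the interval.

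**With a Day 1 baseline added**
- No gap: 24, 48 and 80 weeks, all in the open-label period.
- Assumed 4-week gap with a parent end-of-study value as baseline: at most 28, 52 and 84 weeks, or 1.17, 1.08 and 1.05 times the label.

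**The case against.** The strongest reply is that the parent baseline was chosen for good reason. It is the only pre-drug reference for former-evolocumab subjects, and it gives the two randomised arms equal elapsed time. That stands, and it is why those tables should be kept.

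A reader might go further and infer that SAP 5.2 contradicts the protocol's safety objectives, which speak of 80 weeks of evolocumab. The documents do not support that. The efficacy objectives in Protocol 1.2 and 1.5 use the same 80-week wording, and section 10.4.1 prescribes the parent baseline for them, so the protocol accepts the two together. Because it sets no rollover baseline for safety variables, none is breached, and the empty SAP section 10 hides no departure on this point.

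It is also fair to say that week 24, 48 and 80 are visit names, and no passage equates them with the length of the change interval. That limits the point to missing labelling, not a wrong label.

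Two features of the plan help in part:
- Results are split by parent arm (SAP 5.3, 9.6.3). This identifies the former-placebo subjects but leaves the placebo weeks in their changes.
- "Physical measurements will be summarized using descriptive statistics at each scheduled visit" (SAP 9.6.6), so Day 1 height and weight may be shown, and mean change since Day 1 could be approximated by subtraction if few data are missing. That Appendix A has no Day 1 column does not rule this out, because its windows assign post-baseline records. Subtraction does not give Tanner shifts or the spread of individual changes. For hormones, SAP 9.6.4 promises only selected parameters at selected visits.

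**Conclusion.** The point holds as a reporting gap that is cheap to close. For HeFH rollovers the nominal intervals are 48, 72 and 104 weeks for growth and Tanner stage and 104 weeks for hormones. In former-placebo subjects 24 of those weeks are on placebo, and no planned change table for these variables isolates their open-label drug period. The figures rest on measurement at parent baseline and on immediate rollover. SAP 5.2 also gives no fallback for a rollover without a parent value, whereas the protocol's efficacy rule does.

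Its reach is limited. All tables are descriptive, no formal HeFH to HoFH comparison is planned, and HoFH is about 10 subjects. The primary endpoint of treatment-emergent adverse events is unaffected, because those events are counted from the first dose in this study. The CK, AST and ALT summaries use multiples of the upper limit of normal, not change from baseline, and are also unaffected. ECG change has the same 104-week nominal interval at week 80, but ECG is an other safety endpoint (Protocol 10.1.1.4), outside the secondary safety objectives. Nothing here supports discarding the parent baseline.

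**What to change.** In SAP 5.2 and 9.6.3:
1. Keep the parent-baseline tables for both HeFH arms. Label them with nominal elapsed time since parent baseline: 48, 72 and 104 weeks for growth and Tanner stage, 104 for hormones.
2. Add a Day 1 baseline summary of height, weight, Tanner stage and hormones for the HeFH arms, with ECG optional. Define this baseline as the latest available value before the first open-label dose, whether from Day 1, rollover screening or the parent end-of-study visit. Use it as the description of change on drug in former-placebo subjects and for reading beside HoFH.
3. Footnote that this is an on-treatment baseline for former-evolocumab subjects, so it cannot show their early drug effects, and that it may predate Day 1 after a rollover gap.

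The cost is SAP wording, a second baseline flag, a few extra descriptive tables and the need to footnote two baselines clearly. No new visits are needed, since Protocol Table 2 already schedules these measurements at the Day 1/parent end-of-study visit.

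As a separate minor clarification, state which cIMT scan is the HeFH baseline. SAP 5.2 points to the parent study, while Appendix A footnote a treats scans up to day 28 as baseline without naming a cohort, and may be meant only as a windowing rule.

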5.3 Other Study Related Definitions

Analytical Study Week Assignments

Analytical windows will be used to assign parameter measurements to study weeks. The algorithm is provided in [Appendix A](#).

Investigational Product (IP)

IP refers to Evolocumab SC 420 mg QM.

Study Cohort

The enrolled subjects consist of two study cohorts: HeFH subjects (roll-over subjects from the parent study of 20120123) and HoFH subjects (new enrolled subjects in this study)

For the HeFH subjects rolled over from the parent study, those subjects will be categorized according to the treatment groups they were randomized to in their parent study. All analyses will be summarized based on the followings:

- Roll-over HeFH subjects randomized to AMG 145 in parent study
- Roll-over HeFH subjects randomized to Placebo in parent study
- De-novo HoFH subjects

Study Exposure Period in months:

Interim analysis

- For ongoing subjects, Study Exposure Period = $(\text{data cutoff date} - \text{Enrollment Date} + 1) / 365.25 * 12$
- For subjects who completed study or early terminated from the study, Study Exposure Period = $[\min(\text{EOS date, data cutoff date}) - \text{Enrollment Date} + 1] / 365.25 * 12$

Primary analysis

- For each subject, Study Exposure Period = $(\text{EOS date} - \text{Enrollment Date} + 1) / 365.25 * 12$

IP exposure period in months:

Interim analysis

- For ongoing subjects, IP Exposure Period = $[\min(\text{Last IP dose date} + 28 \text{ days, data cutoff date}) - \text{Study Day 1} + 1] / 365.25 * 12$
- For subjects who completed study or early terminated from the study, IP Exposure Period = $[\min(\text{Last IP dose date} + 28 \text{ days, EOS Date, data cutoff date}) - \text{Study Day 1} + 1] / 365.25 * 12$

Primary analysis

- IP Exposure Period = $[\min(\text{Last IP dose date} + 28 \text{ days, EOS Date}) - \text{Study Day 1} + 1] / 365.25 * 12$

Treatment Emergent Adverse Event (TEAE)

Treatment emergent adverse events are events categorized as Adverse Events (AEs) starting on or after first dose of investigational product as determined by

“Did event start before first dose of investigational product” equal to No or missing on the Events eCRF and up to and including 30 days after the last dose of investigational product or the EOS date or the data cutoff date, whichever is earlier for interim analysis. For primary analysis, treatment emergent adverse events are events categorized as Adverse Events (AEs) starting on or after first dose of investigational product as determined by “Did event start before first dose of investigational product” equal to No or missing on the Events eCRF and up to and including 30 days after the last dose of investigational product or the EOS date, whichever is earlier. Any AE that cannot be defined clearly as a TEAE will be considered a TEAE in the database.

Reflexive Approach for LDL-C and VLDL-C

For all analyses related to LDL-C and VLDL-C, unless specified otherwise, the following reflexive approach will be used. When calculated LDL-C is less than 40 mg/dL or triglycerides > 400 mg/dL, the UC LDL-C value from the same blood sample will be used instead of calculated LDL-C and the UC VLDL-C value from the same blood sample will be used instead of calculated VLDL-C, if available.

6. Analysis Sets

The full analysis set (FAS) includes all subjects with HeFH from parent study 20120123 who are enrolled **and dosed** and all subjects with HoFH who are enrolled and dosed in this study.

Unless specified otherwise, the FAS will be the default analysis set in this study.

7. Planned Analyses

